15.6 Economic Evaluation

In order to estimate which of the three treatment regimes ((i) total discontinuation, ii) seasonal discontinuation, and iii) continuing azithromycin) is most cost-effective, an economic evaluation will be undertaken.

In line with the National Institute for Health and Clinical Excellence (NICE) technology evaluations manual⁶⁷, costs will be estimated from an NHS perspective. Specifically, intervention costs (for each of the three treatment options) will be estimated from trial treatment data (dose, frequency of administration, etc.) along with COPD related costs for hospital admissions, primary care consultations and medication data.

The main measure of effect in the economic analysis will be the EQ-5D-5L (patient self-report data requested at baseline and follow-up trial visits), as this will enable quality adjusted life year (QALY) scores to be estimated.

A Health Economic Analysis Plan (HEAP) will be developed prior to analysis. This will detail the methods to be used to estimate the incremental cost and effect (QALY gain) associated with i) total discontinuation and ii) seasonal discontinuation, both compared to continuing azithromycin. For each discontinuation option, net benefit will be estimated at a threshold value e.g. £20,000 per QALY, where a positive value would indicate discontinuation was estimated to be cost-effective. The associated level of uncertainty will also be estimated.

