From a risk perspective, azithromycin is a key target of stewardship programs and is a World Health Organisation (WHO) Watch group antibiotic.¹⁰ Long-term use individually and at scale does increase antimicrobial resistance (AMR) for the individual and wider community respectively.^{11,12} Use of azithromycin is associated with increased risk of cardiovascular death as evidenced from pharmacoepidemiology studies.^{13,14} Given that people with COPD have increased cardiovascular risk,¹⁵ there is need for long-term follow-up for COPD patients on treatment. Azithromycin can also cause hearing loss.⁴ People with COPD often have multimorbidity, frailty and polypharmacy¹⁶⁻¹⁸ and the risk of further isolating people due to difficulties in communication caused by prescribed medicines needs urgent evaluation. Multimorbidity may also impact relative benefits gained vs risks of chemoprophylaxis as suggested by NICE.¹⁹ A further concern with long-term azithromycin treatment is potential impact on non-tuberculous mycobacteria (NTM) resistance.^{20,21} This is important as azithromycin is a valuable antibiotic used in the treatment of NTM.

5.1.1 Seasonality of COPD exacerbations

COPD exacerbations display strong seasonality in temperate climates such as the UK, as evidenced by primary care usage, hospitalisations, mortality data and seasonal bed pressures.²²⁻²⁸ In today's clinical practice, whether a shorter seasonal course of azithromycin is comparable, in clinical effectiveness, to long-term chemoprophylaxis is unknown, although seasonal use of azithromycin is recommended as a de-escalation approach from continued use in some local trust guidelines.²⁹ A historic trial of seasonal tetracyclines chemoprophylaxis vs placebo in chronic bronchitis, showed significant reduction in exacerbations in susceptible patients (those with >1 exacerbation/winter).³⁰ There are no seasonal chemoprophylaxis trials of any antibiotic undertaken in the modern era of COPD management.

5.1.2 COPD subgroups

Three azithromycin chemoprophylaxis trials performed post-hoc, subgroup analyses to identify factors associated with treatment responsiveness to azithromycin. Han *et al*

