7.8 Trial Outcome Measures

7.8.1 Primary outcome measure

Time to first COPD exacerbation.

7.8.2 Secondary outcome measures

Data pertaining to secondary outcomes will be collected over the entire trial follow-up (i.e. inclusive of time on IMP and if needed off IMP):

- Number/rate of exacerbations (and differentiation by severity of exacerbations, i.e. requirement of hospitalisation)
- Length of exacerbation-free status
- Antibiotics and/or corticosteroids use for respiratory indication
- Symptoms/impact: CAT score and cough visual analogue score (VAS)
- Health status (quality of life measured by change in EQ-5D-5L)
- Mortality (all cause and specific)
- Healthcare utilisation (for health economic analysis)
- Adverse events of special interest (AESI) (including cardiovascular and hearingdefined as new prescription of hearing aids, liver function test (LFT) dysfunction), serious adverse events (SAEs)
- Sputum culture results, if clinically indicated and sample via routine clinical care to local lab. Record if positive result (i.e. name of organism cultured only, not cfu/ml). If multiple sent, most recent one to trial visit should be used.
- Adherence to trial medication.

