This is a 2-item instrument that is used to screen for anxiety and will be used at baseline. It is often used in primary care as it is simple and easy to do. It comprises the first 2 items of the GAD-7 questionnaire. It is scored from 0-6 with a higher score indicating an underlying anxiety disorder. A score \geq 3 is suggestive of an underlying anxiety disorder and need for further investigation. The GAD-2 has been validated in many studies and has reasonable sensitivity of 83% and specificity of 92% similar to the GAD-7.⁵⁷ If the GAD-2 screening test is suggestive of a possible anxiety disorder and this is not already a known diagnosis, the participant will be advised to see their GP about it. Please refer to the TPM.

10.4.16 Healthcare usage

Information regarding healthcare usage (hospitalisation and primary care consultations for example) will be recorded.

10.4.17 Adherence

Adherence will be evaluated during trial follow-up by estimated compliance, whereby participants will be asked to return trial bottles and unused medication to the trial research team at their appointment(s).

10.4.18 Adverse events/SAEs

Adverse events (AEs) and SAEs will be assessed at baseline and during trial follow-up. AEs will be recorded within the medical notes; SAEs will be reported to the central OPACE trial team for CI review. For more information see section 11.

10.4.19 Self-Rated Health Status (SHS) (approximately 1 min)

This will be assessed at baseline and at the end of trial and will be used in the Study Within a Project (SWAP) as described in the Appendix B. The SHS is a one question assessment of health status recommended by NICE as a screening tool for frailty in patients. It asks patients to rate their health on a scale of 0-10. A score of 6 or less indicates frailty.^{19, 58}

10.4.20 Clinical Frailty Scale (CFS) (approximately 1 min)

This will be assessed at baseline and end of the trial as part of the SWAP as described in Appendix B. The Clinical Frailty Scale (CFS) is a tool used in clinical practice in older patients to provide an assessment of capability (in last two weeks) which may be helpful to indicate frailty. It can be conducted by any appropriately trained healthcare professional.⁵⁹

10.4.21 Electronic Frailty Index (eFI) (approximately 2 min):

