11.3 Expected Adverse Events/Serious Adverse Events (AE/SAE)

Exacerbations of COPD or hospital admissions as a consequence of exacerbations of COPD will **not** be considered as AEs or SAEs because they are primary and secondary outcomes for the trial. These will be recorded as part of the trial outcomes, and therefore not reported as AEs or SAEs.

Adverse events of special interest (AESI) that will be evaluated in the trial include those below. These may also require SAE reporting.

New major adverse cardiovascular events (MACE):
Myocardial infarction
Stroke
Cardiovascular death
Development of arrhythmias
Hearing (for example new prescription of hearing aids)
LFT dysfunction

These will be recorded separately to all other AEs, to enable ease of data analysis.

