13 EVALUATION OF RESULTS (DEFINITIONS AND RESPONSE/EVALUATION OF OUTCOME MEASURES)

13.1 Response criteria

13.1.1 Exacerbations Primary endpoint is time to first exacerbation.

Secondary endpoint is number/rate and severity of exacerbations (i.e. moderate and/or severe). These will be patient reported and recorded in the database.

13.1.2 Survival

This will be measured from the date of randomisation and will be reported for all deaths. The cause of death is to be recorded in all instances where possible. All-cause mortality, respiratory/COPD-related and cardiovascular mortality will be collated.

13.1.3 Quality of life, anxiety and depression

EQ-5D-5L will be used to assess quality of life. GAD-2 and PHQ-2 will assess levels of anxiety and depression.

13.1.4 Symptoms

These will be assessed by the CAT score and cough VAS.

The self-rated health status (SHS) will assess level of frailty in participants.

Healthcare usage for their COPD will be assessed throughout their trial follow-ups.

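### The economic evaluation costs care for COPD but not NHS care for the azithromycin harms the protocol itself names, so incremental cost leaves out part of the trade-off under test

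*Protocol*

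**What the plan says.** Section 15.6 states that "costs will be estimated from an NHS perspective". It then specifies the components: the cost of each treatment option, "along with COPD related costs for hospital admissions, primary care consultations and medication data". Net benefit is to be computed at a threshold such as £20,000 per QALY, with QALYs from the EQ-5D-5L. A Health Economic Analysis Plan (HEAP) is to set out the estimation methods.

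Other sections describe healthcare use differently:

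- Section 13.1.4: "Healthcare usage for their COPD will be assessed throughout their trial follow-ups".
- Section 7.8.2 lists, with no disease limit, "Healthcare utilisation (for health economic analysis").
- Section 10.4.16: "Information regarding healthcare usage (hospitalisation and primary care consultations for example) will be recorded".

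On the harms of continuing treatment, section 5.1 says "Use of azithromycin is associated with increased risk of cardiovascular death as evidenced from pharmacoepidemiology studies" and "Azithromycin can also cause hearing loss". Section 11.3 makes myocardial infarction, stroke, cardiovascular death, arrhythmia and LFT dysfunction adverse events of special interest (AESIs), together with "Hearing (for example new prescription of hearing aids").

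**The concern.** The trial weighs two kinds of harm. Stopping azithromycin may bring more exacerbations; continuing it may bring cardiovascular, hearing or liver harm. The first kind is COPD-related and enters the cost total. The second is not COPD-related, and no cost line in section 15.6 covers it.

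Take two participants. One stops azithromycin and is admitted with an exacerbation; that admission is costed. The other continues and is admitted with a myocardial infarction, or is fitted with NHS hearing aids; nothing is added. The QALY side has no such filter, since the EQ-5D-5L is a generic instrument and deaths of any cause are collected. The same net-benefit formula could therefore count the health loss from a stroke but not the NHS spending on it.

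What is at stake is secondary objective 7, cost-effectiveness, for both discontinuation comparisons. The primary analysis is not affected.

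**Working it through.** There is no stated figure to reproduce. The check is of which costs the written rule includes, and what leaving the others out does to net benefit.

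**Step 1. What the rule includes.**

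| Item of NHS care | Where the protocol names it | Costed under 15.6 as written? |
|---|---|---|
| Exacerbation admission, consultation or medication | 7.8.2, 10.4.1 | Yes |
| Trial treatment | 15.6 | Yes |
| Myocardial infarction, stroke, arrhythmia | 11.3 | No |
| Hearing aids | 7.8.2, 11.3 | No |
| Liver dysfunction | 7.8.2, 11.3 | No |
| Infections other than exacerbations | 8.8 | No |

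**Step 2. Effect on net benefit.** For a discontinuation arm against continued azithromycin:

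NB = 20,000 × ΔQALY − ΔCost, where ΔCost = mean cost when discontinuing − mean cost when continuing.

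Let H be the mean NHS cost per participant of the named AESIs, and O the mean cost of all other non-COPD care. Section 15.6 leaves out both, so

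NB (all care) − NB (as written) = (H continuing − H discontinuing) − (O discontinuing − O continuing).

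- If H is higher on continued treatment and O is equal, the written rule understates the net benefit of discontinuing.
- If stopping an antibiotic raises the cost of other infections, so that O is higher when discontinuing, the second term pulls the other way.
- If neither H nor O differs between arms, the expected effect is zero.

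**Step 3. Conversion to QALYs.** An omitted difference of £X per participant equals X / 20,000 QALY, so £100 equals 100 / 20,000 = 0.005 QALY.

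**Step 4. Illustration only.** The documents give neither an excess risk nor a unit cost. The values below are assumptions, and O is taken as equal between arms. Omitted cost = excess risk over follow-up × cost per event.

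| Assumed excess risk on continued treatment | £1,000 per event | £3,000 per event | £6,000 per event |
|---|---|---|---|
| 0% | £0 | £0 | £0 |
| 1% | £10 (0.0005 QALY) | £30 (0.0015) | £60 (0.003) |
| 2% | £20 (0.001) | £60 (0.003) | £120 (0.006) |
| 4% | £40 (0.002) | £120 (0.006) | £240 (0.012) |

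The assumed range is thus £0 to £240 per participant, or 0 to 0.012 QALY. It would matter only where the arms differ little in cost and QALYs.

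**Step 5. Are the data there?** Section 10.5 plans hospital episode and mortality data up to the common end date, without a COPD limit. Section 10.6 schedules healthcare usage at 3, 6 and 12 months and about six-monthly after that. AESI forms are a weaker source. Section 11.1.4.1 ends adverse event recording 28 days after trial medication is stopped, while section 11.1.7 runs it to the end of active follow-up. Section 8.7 stops trial medication at three or more exacerbations in a year, which may be reached more often in one arm than another. Costing from AESI forms alone could therefore give follow-up that differs by arm.

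**The case against.** The strongest objection is that the HEAP will set the costing methods, so scope is not yet decided. This does not answer the point: section 15.6 already names the cost components and restricts them to COPD. It is a stated rule, not a gap. It is fair that the HEAP can widen the scope, since sections 7.8.2, 10.4.16 and 10.5 already provide for wider data.

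Three stronger readings are tempting, and the objection to each stands:

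- *A reader might infer that the scope contradicts the NHS perspective.* A perspective says who pays, not which diseases are costed, so there is no contradiction.
- *A reader might infer that net benefit is shown to be biased against discontinuation.* The documents do not show this. Section 8.8 foresees other infections, whose costs also fall outside COPD-related care and could offset the omitted AESI costs. Some of the cardiovascular harm cited in section 5.1 is death, which is chiefly a QALY loss.
- *A reader might compare the omission with the drug cost in section 6,* where £450,000 / 60,000 = £7.50 per prescription. That figure covers all azithromycin prescriptions in England, and section 9.1.1.1 notes that the drug is licensed for treating infections. It is not the price of a month of prophylaxis, so a ratio to it has no sound basis.

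It can also be said that adding only suspected azithromycin harms swaps one selective scope for another. That is a fair caution and is why an all-cause figure should stand beside the base case.

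**Conclusion.** The concern holds in limited form. As written, incremental cost includes the main expected harm of stopping and leaves out NHS care for the harms of continuing that the protocol itself lists, while the QALYs can reflect those harms. Net benefit can be biased against discontinuation if azithromycin causes an excess of these events. Neither that excess nor the net direction can be established from the protocol, and the size rests wholly on assumed event rates and unit costs. Sections 13.1.4 and 15.6 also need to be reconciled with 7.8.2 and 10.4.16, so that sites know what to collect. If collection follows 13.1.4, non-COPD primary care use may not be recorded, and the planned linkage to hospital and mortality records would not supply it later. The change is worth making because it is cheap and bears on a named secondary objective.

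**What to change.** 1. In section 15.6 and the HEAP, define base-case cost as intervention cost, plus COPD-related care, plus NHS care for the named AESIs (cardiovascular events, arrhythmia, hearing, liver dysfunction), in all three arms.
2. Cost admissions from linked hospital records over full follow-up to the common end date, not from AESI forms alone.
3. Take hearing-aid and primary-care items from the healthcare-usage record, collected for the same period in every arm whether or not trial medication has stopped. Hearing aids are not among the examples in section 10.4.16 and should be added explicitly.
4. Report all-cause admission cost as a sensitivity analysis. This shows whether other non-COPD admissions, including those for other infections, change the answer.
5. Reconcile the COPD limit in section 13.1.4 with sections 7.8.2 and 10.4.16.

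The cost is some wording, a few extra unit costs and an added usage item. Rare expensive events will add slightly to the variance of mean cost. Linked admissions and scheduled healthcare-usage collection are already planned.

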15.7 Definition of the End of the Trial

The end of the trial will be the date of the last patient's last visit (LPLV).

16 DATA HANDLING AND RECORD KEEPING

16.1 CRF

All data will be transferred into a Case Report Form (CRF) which will be de-identified. All trial data in the CRF must be extracted from and be consistent with the relevant source documents.

Electronic case report forms (eCRFs) will be used to collect the data, all data will be entered onto a secure electronic database. The database, which will be MHRA and GDPR compliant, will be secured by appropriate access control and password protection. All trial data in the eCRF must be extracted from and be consistent with the relevant source documents. The eCRFs must be completed by the investigator or designee in a timely manner. It remains the responsibility of the investigator for the timing, completeness and accuracy of the eCRF. The eCRF will be accessible to trial coordinators, data managers, the investigators, Clinical Trial Monitors, Auditors and Inspectors as required. In the situation where the database is down or there are other problems that mean eCRFs cannot be used, the data will be recorded on paper CRFs as a back-up. Data provided to the central coordinating team will be checked for errors, inconsistencies, and omissions. If missing or questionable data are identified, the central coordinating team will request that the data be clarified.

16.2 Source Data

To enable peer review, monitoring, audit and/or inspection the investigator must agree to keep records of all participating participants (sufficient information to link records e.g. CRFs, hospital records and samples), all original signed informed consent forms and copies of the CRF pages.

Source data are:

- Medical records
- Signed Informed Consent forms
- Online test result systems
- Participant diaries for COPD flare-ups
- Questionnaire pack
- NHS digital data
- Reported SAE forms

16.3 Data Protection & Participant Confidentiality

All investigators and trial site staff involved in this trial must comply with the requirements of the Data Protection Act 2018 and Trust Policy with regards to the collection, storage, processing, transfer and disclosure of personal information and will uphold the Act's core principles.

Trial participants will provide explicit consent to the use of identifiable data for the purposes of the conduct of the trial.

Patient identifiable data (PID) will be accessible to limited GCP-trained members of the trial team including central pharmacy to enable dispensing of trial medication (information required for this: name and contact details: home address and postcode, telephone number and email address where applicable to facilitate dispense and courier of trial medication). A limited number of GCP-trained members of the OPACE trial management team within the Cambridge Clinical Trials Unit, may need to access PID (name, date of birth, gender, NHS number or equivalent, home address and postcode, telephone number and email address) where applicable as required for trial purposes. It is necessary to 1) perform linkage to national datasets (NHS Digital and equivalent in devolved administrations and 2) if needed to aid central pharmacy coordination of home delivery of trial medication. Sponsor monitors, auditors and inspectors may need to access PID data as part of their process of trial monitoring.

All PID downloaded from NHS Digital and the equivalent national health record organisations will be stored securely on the University of Cambridge, School of Clinical Medicine Secure Data Hosting Service (SDHS). The SDHS is registered and approved under the NHS Digital Data Security and Protection Toolkit and is ISO 27001 certified.

17 DATA MONITORING COMMITTEE/TRIAL STEERING COMMITTEE

Data Monitoring Committee

The ethical and safety aspects of the trial will be overseen by an independent DMC. IDMC meetings will be timed so that reports can be fed into the TSC meetings. Full details of the IDMC membership and remit can be found in the IDMC Charter. Minutes will be taken at these meetings, which will be signed by the Chair of the Committee.

Trial Steering Committee

The TSC provides overall supervision for the trial on behalf of the Sponsor and Funder (NIHR), to ensure that it is conducted in accordance with the protocol and GCP and to

provide advice through its independent chairman. The committee will aim to convene at regular intervals to review the data and discuss the progress of the trial at a top level, including adherence to the protocol, participant safety and considerations for new information, specified in the TSC charter. Full details of the TSC membership and remit can be found in the TSC charter. Minutes will be taken at these meetings, which will be signed by the Chair of the Committee.

Trial Management Group

The trial project management group (TMG)'s role is to oversee the day to day running of the trial, data management and monitoring. It will be set up and follow the terms and conditions as per a CTIMP charter template for a trial management group. It is made up of the CI(s) and other grant holders as appropriate, the trial coordinator and other senior members of the Cambridge Clinical Trials Unit (CCTU) and other members of the respiratory/trials community that will provide advice and collaboration to enable facilitation of the trial. TMG meetings will take place on a weekly basis to discuss progress of the trial and any issues that require resolving. Minutes will be taken at these meetings.

18 ETHICAL & REGULATORY CONSIDERATIONS

18.1 Ethical Committee Review

Before the start of the trial or implementation of any amendment we will obtain approval of the trial protocol, protocol amendments, informed consent forms and other relevant documents e.g., advertisements and GP information letters if applicable from the REC. All correspondence with the REC will be retained in the Trial Master File/Investigator Site File.

Annual reports will be submitted to the REC in accordance with national requirements. It is the CI's responsibility to produce the annual reports as required.

18.2 Regulatory Compliance

The trial will not commence until a Clinical Trial Authorisation (CTA) is obtained from the MHRA. The protocol and trial conduct will comply with the Medicines for Human Use (Clinical Trials) Regulations 2004 and any relevant amendments.

Development Safety Update Reports (DSURs) will be submitted to the MHRA in accordance with national requirements. It is the CI's responsibility to produce the annual reports as required.

